3.6 Changes to Analyses Planned in the Protocol

This SAP will be updated as necessary if any changes in the protocol occur due to the expected protocol amendment impacting the SAP.

4 **DEFINITIONS AND DERIVED DATASETS**

Table 1. Terminology and Definition

| Terminology | Definition |
|----------------------------|--|
| Study Medication | SPN-810 or the matching placebo. |
| Study Day | The first dose date (Day 1) is defined as the date on which a subject took the first dose of double-blind study medication (SM), Other study days are defined relative to the Study Day 1. For visits prior to the first dose of the SM, Study Day is calculated as Visit Date – Day 1. For visits after the first dose, Study Day is calculated as Visit Date – Day 1 +1. |
| Enrolled | Subject has provided signed informed consent. |
| Randomized | Subject is assigned with the kit number for the SM. |
| Completer for the Study | Subject who completes the maintenance period (Visit 6). |
| Baseline | Unless specified otherwise, baseline is defined as the non-missing value collected most recent to and before the time of the very first dose of the SM. For example, Visit 3 CGI-S, CHQ-PF28, PSI-4-SF, and SNAP-IV are collected prior to the first dose. Their values are considered baseline for the covariate analysis. |
| Baseline Period | For subject daily IA diaries, on and prior to Visit 3 (inclusive, ≤Day 1). |
| Prior Medication | Medication collected on the Prior/Concomitant Medication CRF, with the start date prior to Study Day 1. |
| Concomitant Medication | Medication collected on the Prior/Concomitant Medication CRF, with end date on/after Study Day 1. |
| Titration Period | For subject daily IA diaries from Visit 3 through Visit 5 (v3< to \leq V5) |
| Maintenance Period | For subject daily IA diaries from Visit 5 through Visit 6 (V5< to \leq V6) |
| Treatment Period | Titration and Maintenance Periods combined |

| Terminology | Definition |
|-----------------|--|
| Derived Dataset | Derived dataset (analysis dataset) is any permanently stored collection of data containing raw and/or derived variables created to support the production of statistical summary tables. Derived variables will be created from the "raw" data. Analysis datasets to be created will include ADEFF (efficacy analysis dataset), ADSL (subject-level analysis dataset), ADAE (Adverse event analysis dataset) and other as appropriate. In deriving ADEFF, the source data include both the episodic diary and evening diary data files. Specifications for derived datasets will be developed which will include the names and definitions of derived variables in the derived SAS datasets. |

5 **EFFICACY AND SAFETY VARIABLES**

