## 3.2.2 Treatment Phase

## 3.2.2.1 Randomization

Inclusion/exclusion criteria will be re-assessed to verify eligibility prior to study randomization at the end of Visit 3 (Randomization). Eligible subjects whose primary caregiver has maintained at least 80% compliance with the IA diary will be randomized. Per the original randomization eligible subjects who complete the baseline period and meet the requirements for the double blind study will be randomized at Visit 3 (Day 1) in a 1:1:1 ratio to receive 18 mg/day, 36 mg/day SPN-810 or placebo and proceed to the titration period, which will be two weeks. However, based on the 810P301 study Interim Analysis result decision, the 18 mg arm was dropped partway through the study. As a result, subjects planned to be randomized to the 18 mg arm will be re-allocated to the 36 mg or placebo arm in a ratio of 2:1.

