# 4.3 Treatments

#### 4.3.1 Treatments Administered

Subjects will take molindone hydrochloride extended-release tablet (SPN-810) or placebo twice each day (BID) with food, in the morning and in the evening, in addition to the stable dose of the optimized ADHD medication determined from the lead-in period. If initiating treatment before noon, patients should start with the morning dose; if after noon, the evening dose.

Subjects will be randomized to one of three treatments at Visit 3. Subjects will be titrated up to the final randomized total daily dose (TDD).

- Reference treatment
  - Treatment 1: Placebo tablets, PO, BID
- Test treatments
  - o Treatment 2: Molindone extended-release tablets, 18 mg TDD, PO, BID
  - o Treatment 3: Molindone extended-release tablets, 36 mg TDD, PO, BID

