#### 4.3.6 Dosing Schedule

During Visit 3, subjects will be randomized to Treatments 1, 2, or 3 and start dosing. Table 2 below presents the details of the dosing schedule for each active treatment group throughout the 6-week treatment phase for this study. Dose reduction will not be permitted in the study.

Treatment			Study Days					
Arm	Final Dose		1-2	3-5	6-8	9-11	12-14	15+
	-	Period*	Т	Т	Т	Т	Т	М
1	Placebo		PBO	PBO	PBO	PBO	PBO	PBO
2	18 mg							
3	36 mg							

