7.1.1 Safety Population

The safety population will include all randomized subjects who received at least 1 dose of study drug and have at least one post-randomization safety measurements.

7.1.2 *Modified Intent-to-treat (mITT) Population*

The modified intent-to-treat population will include all subjects who received at least 1 dose of study drug and have a baseline IA frequency \geq 6 per week and at least 1 valid post-randomization assessment of frequency of IA behaviors based on IA diary entry. Subjects will be analyzed according to the treatment they were randomized to.

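### The SAP counts Day 1, the day of randomisation and first dose, as a baseline diary day, so the primary endpoint's denominator and entry to the mITT population rest partly on post-randomisation data (minor; one-line fix)

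*SAP*

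**What the plan says.** The terminology table in SAP Section 4 sets three rules that meet at Visit 3:

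- **Day 1:** "The first dose date (Day 1) is defined as the date on which a subject took the first dose of double-blind study medication (SM".
- **Diary Baseline Period:** "For subject daily IA diaries, on and prior to Visit 3 (inclusive, ≤Day 1".
- **Diary Titration Period:** "For subject daily IA diaries from Visit 3 through Visit 5 (v3< to" Visit 5, so it starts the day after Visit 3.

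For other measures the table's general rule is that "baseline is defined as the non-missing value collected most recent to and before the time of the very first dose of the SM". That rule opens with a proviso allowing exceptions.

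The protocol fixes the events of the day. Section 3.2.2.1 says that "subjects who complete the baseline period and meet the requirements for the double blind study will be randomized at Visit 3 (Day 1". Section 4.3.6 says "During Visit 3, subjects will be randomized to Treatments 1, 2, or 3 and start dosing". Table 2 in that section labels Study Days 1-2 as titration. Section 4.3.1 lets the first dose fall in the morning or the evening: "If initiating treatment before noon, patients should start with the morning dose; if after noon, the evening dose". Section 4.2.3 lists a post-dose adverse event assessment at Visit 3. The evening diary reviews the whole day (SAP Section 5.1).

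B has two main uses. SAP Section 5.1 makes it the denominator of the percent change. SAP Section 7.1.2 admits to mITT only children who "received at least 1 dose of study drug and have a baseline IA frequency" of at least 6 per week, and Section 7.8.1 bases the primary analysis on mITT.

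**The concern.** A baseline that both scales the outcome and decides who is analysed should be fixed before assignment. Here one of its days ends after randomisation and, for children dosed that morning, after the first dose as well. No SAP rule separates Day 1 entries made before and after either event.

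Two things are at stake. First, if treatment changes behaviour on Day 1, B is altered in the treated arm and the percent change is altered with it. Second, a child near the cut can enter or leave the primary population because of a day that treatment may already have affected. The second matters more in principle, because membership of the primary population could then depend, even slightly, on arm.

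The same B also feeds the responder analyses (SAP 7.8.6.2), the covariate-adjusted analysis (7.8.4) and the baseline variable `bwk` in the imputation models (7.8.2).

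**Working it through.** **1. Inputs from the documents.** Diary compliance for randomisation is 80%, at least 12 of 15 days (protocol Table 1, footnote e). Check: 12/15 = 0.80. Baseline may be extended by up to 15 days (protocol 3.2.1.2), giving at most 30. Frequency is (SUM/DAY) × 7, and the endpoint is 100 × (T − B)/B (SAP 5.1). The mITT cut is 6 per week.

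**2. Where Day 1 would otherwise fall.** The visit schedule puts Visit 2 at Day −15. In SAP day numbering the day before Day 1 is Day −1, so Days −15 to −1 are exactly 15 days. The required window is complete without Day 1.

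**3. Weight of Day 1 in B.** With d earlier diary days the weight is w = 1/(d + 1). The smallest count for mITT entry is the smallest SUM with (SUM/DAY) × 7 ≥ 6.

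| d | w | Smallest SUM, Day 1 excluded | Smallest SUM, Day 1 included |
|---|---|---|---|
| 12 | 1/13 = 7.7% | 11 | 12 |
| 15 | 1/16 = 6.3% | 13 | 14 |
| 30 | 1/31 = 3.2% | 26 | 27 |

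**4. Day 1 alone can decide entry.**

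- 13 behaviours in 15 days: 13/15 × 7 = 6.07. With none on Day 1: 13/16 × 7 = 5.69, so the child is excluded.
- 12 behaviours in 15 days: 12/15 × 7 = 5.60. With two on Day 1: 14/16 × 7 = 6.13, so the child is included.

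**5. Effect on the endpoint.** If Day 1 counts fall by a fraction r, B becomes B(1 − rw). The documents give neither r nor T/B, so I assume T/B = 0.6, a true change of −40.0, with d = 15:

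- r = 10%: 100 × (0.6/0.99375 − 1) = −39.6, a shift of 0.4 points
- r = 20%: 100 × (0.6/0.9875 − 1) = −39.2, a shift of 0.8 points
- r = 50%: 100 × (0.6/0.96875 − 1) = −38.1, a shift of 1.9 points

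At r = 50% the shift runs from 2.4 points (d = 12) to 1.0 (d = 30). Every shift is toward no effect.

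**6. Effect on mITT entry.** This is a simulation under assumed negative-binomial daily counts (dispersion 1) with d = 15. For children with a true rate of 6 per week, including Day 1 changes status as follows:

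| Day 1 drug effect | Moved out | Moved in | Included in mITT |
|---|---|---|---|
| None | 4.3% | 3.3% | 48.3% |
| 30% reduction | 5.0% | 1.9% | 46.1% |

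The first row is counting noise that both arms share. Only the difference between rows can act by arm: 48.3 − 46.1 = 2.2, about 2 percentage points. With a 10% effect it is about 0.7. With a 30% effect it is about 1 point at 10 per week and about 0.1 at 15 per week. The documents give no distribution of baseline rates, so the share of children near the cut is unknown.

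**The case against.** The strongest reply is that diaries are kept by calendar day, so some rule must place the boundary day. Behaviour before the clinic visit on Day 1 is genuinely pre-randomisation, and a child seen after noon takes the first dose in the evening. Moving Day 1 to titration would put some pre-dose behaviour into T. This stands: Day 1 is a mixed day. But excluding it from both periods avoids the problem, and the protocol's own dosing table already calls it titration.

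Three stronger readings are tempting, and the documents do not support them.

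- **That the SAP contradicts its own baseline definition.** The general rule allows for exceptions, and the diary row is one. What can fairly be said is that the exception is unexplained and does not fit protocol Table 2 or Section 3.2.2.1.
- **That caregiver expectancy on Day 1 moves children out of mITT by arm.** The trial is double-blind with matching placebo (protocol 4.3.8), so expectancy acts in both arms. Only a same-day drug effect could act by arm. Active dosing starts at 3 mg/day (protocol 3.2), and the documents give no evidence of a large effect within hours.
- **That all the switching of mITT status reflects bias.** Most of it is present with no Day 1 effect at all.

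The ITT repeat in SAP 7.8.1 removes the cut at 6 per week, which helps with membership. It uses the same B, so it does not remove the effect on the denominator.

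**Conclusion.** The point holds as a minor flaw of definition. As written, 3.2% to 7.7% of the baseline that scales the primary endpoint and decides entry to the primary population comes from a day that ends after randomisation.

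A reader might infer that this inflates the false-positive rate or favours the drug. It does neither in the cases considered. If the drug has no Day 1 effect, B and mITT membership have the same distribution in both arms, and the rank-sum comparison stays valid with slightly more noise. If the drug lowers Day 1 counts, B falls in the active arm and the measured benefit shrinks slightly, while borderline active-arm children leave mITT slightly more often than placebo children.

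The sizes rest on assumed values: T/B of 0.6, Day 1 reductions of 10-50%, and the count model above. The weights, the entry thresholds and the two worked children need no such assumption; they follow from the SAP's formulas once the diary days and counts are set. The case for acting is that membership of the primary population should not depend on post-assignment data when avoiding this costs almost nothing.

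**What to change.** In the SAP Section 4 terminology table, define the diary Baseline Period as days before Day 1 (study day ≤ −1). Protocol 4.3.6 expects the first dose at Visit 3; if it falls later, end baseline before the earlier of the two dates, so that no day on or after randomisation enters B. Apply this one definition to B, the mITT cut, the responder analyses, the covariate-adjusted analysis and `bwk`.

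State where Day 1 goes: either excluded from both periods, or assigned to titration in line with protocol Table 2. Report the current definition as a sensitivity analysis.

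The cost is one line in the SAP, one line in the specification of the efficacy analysis dataset (ADEFF), and one fewer baseline day per child. The 15 days of diary use required before Visit 3 remain. There is no material downside.

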5.1 Primary Efficacy Variable

The primary efficacy endpoint is percent change (PCH_T) in the frequency (unweighted score) of IA behaviors per 7 days in the treatment (titration and maintenance) period relative to the Baseline period calculated over the number of days with non-missing IA diary data.

PCH_T will be calculated as 100 x (T – B)/B, where T and B are IA behavior frequencies per 7 days during the treatment period and baseline period, respectively. The IA behavior frequency per 7 days is defined as (SUM/DAY) x 7, where SUM is the total of the IA behaviors reported in the subject IA diary, and DAY is the number of days with non-missing IA score in the subject IA diary during the specified study period.

This primary efficacy variable will be based on a checklist of 15 IA behaviors collected in an electronic IA diary. The IA diary comprises two parts: 1) an episodic diary that will be used by the primary caregiver (or alternate) to enter events as soon as possible after they are observed; and 2) an evening diary that will prompt the caregiver to review events for the day and to enter any events that were not previously captured. Each event will be characterized by a checklist of 15 observed behaviors: Yelling, Screaming, Threatening, Scratching, Throwing, Slamming, Hitting Self, Arguing, Cursing, Name Calling, Shoving, Hair Pulling, Fighting, Hitting Others, and Kicking Others. The checklist will indicate whether each behavior was observed (coded 1) or was not observed (coded 0) during the incidence of an event. Each day can have multiple events. A day can have no event, as can be attested in the evening diary. In this case, if no event is reported

during a day, and the evening diary confirms this, the daily event score for that subject will be 0 for each of the 15 IA variables. Behaviors not on this list will not be captured.

5.2 Secondary Efficacy Variables

5.2.1 *Key Secondary Variables*

The key secondary efficacy variable is the change from Baseline (Visit 3) to Visit 6 in Investigator CGI-S score.

- 5.2.2 Additional Secondary Variables
 - 1. Investigator CGI-I score at Visit 6
 - 2. CHQ-PF28 score at Visit 6
 - Physical functioning summary score
 - Psychosocial health summary score
 - 3. PSI-4-SF (Parenting Stress Index Short Form) score at Visit 6 in
 - Parental Distress
 - Parent-Child Dysfunctional Interaction
 - Difficult Child
 - 4. Caregiver CGI-I score at Visit 6
 - 5. SNAP-IV ADHD (Swanson, Nolan and Pelham-IV Rating Scale for Inattention, hyperactivity-impulsivity and oppositional defiant disorder measured) score at Visit 6 in
 - Inattention ratings
 - Hyperactivity/Impulsivity ratings
 - Oppositional Defiant Disorder
 - Combined subscale ratings
 - 6. % of responders with ≥50% reduction in the frequency of IA behaviors from baseline to the treatment period
 - % of responders with ≥30% reduction in the frequency of IA behaviors from baseline to the treatment period

The CGI scale was developed to provide a brief, stand-alone assessment of the clinician's view of a subject's global functioning prior to and after administration of a SM (Guy 1976). Severity of illness (CGI-S) and global improvement (CGI-I) are both rated on a scale of 1 to 7 with 7 being "extremely ill" or "very much worse", respectively. Successful therapy is indicated by a lower overall score in subsequent testing. Investigators should consider their total clinical experience with children who have IA associated with ADHD and rate how severe the subject's condition is at the time.

- CGI-I, relative to the condition at Visit 3, will be evaluated by the caregiver and by the Investigator at each post baseline visit on a 7-point scale with 1=Very much improved, 2=Much improved, 3=Minimally improved, 4=No change, 5=Minimally worse, 6=Much worse, and 7=Very much worse.
- CGI-S will be evaluated by the Investigator at –each visit on a 7-point scale with 1=Normal, 2=Borderline ill, 3=Mildly ill, 4=Moderately ill, 5=Markedly ill, 6=Severely ill, and 7=Extremely ill.

The Child Health Questionnaire Parent Form 28-item (CHQ-PF28) (Protocol Appendix 10.11) is evaluated by the primary caregiver at Visit 3 and Visit 6 for the subject's health status and health related quality of life. CHQ-PF28 items have four, five, or six response options, divided over eight multi-item scales (Physical Functioning [PF, Q2.1a–2.1c], Behavior [BE, Q5.1a-5.1c, Q5.2], Mental Health [MH, Q6.1a-6.1c], Self-Esteem [SE, Q7.1a-7.1c], General Health Perceptions [GH, Q1.1, Q8.1a-8.1c], Parental Impact - Emotional [PE, Q9.1a-9.1b], Parental Impact - Time [PT, Q9.2a-9.2b], and Family Activities [FA, Q9.3a-9.3b]) and five single item concepts (Global Health [GGH, Q1.1], Role/Social Limitations - Emotional/Behavior [REB, 3.1], Role/Social Limitations - Physical [RP, Q3.2], Bodily Pain/Discomfort [BP, Q4.1], Global Behavior [GBE, Q5.2], Family Cohesion [FC, Q9.4], and Change in Health [CH, Q8.2]). In addition, the individual scale scores will be aggregated to derive 2 summary component scores: the physical functioning and psychosocial health summary scores. Range on subscales and the overall scale is 0–100, where 0 is the worst possible health state and 100 the best possible health state. Details for item and multi-item scale scoring, calculation of standardized scores and Aggregate Physical and Psychological Summary Scores can be found in the Child Health Questionnaire (CHQ) Scoring and Interpretation Manual (HealthActCHQ).

The Parenting Stress Index – Short Form (**PSI-4-SF**) is a 36-item self-report measure of parenting stress at Visit 3 and Visit 6. Three subscales (Parental Distress [PD: Q1-12], Parent-Child Dysfunctional Interaction [P-CDI: Q13-24], and Difficult Child [DC: Q25-36]) consist of 12 items each. Parents use a 5-point scale to indicate the degree to which they agree with each statement. The subscale score is the sum of the respective item scores. "Total Stress" score is the sum of the 3 subscale scores. The subscale will be set to missing if 2 or more (>1) item scores in the subscale are missing. Total Stress score is set to missing if 1 or more subscale score is missing.

The **SNAP-IV** (Protocol Appendix 10.7) rating scale includes 18 ADHD and 8 oppositional defiant disorder (ODD) symptoms as specified in the DSM-IV-TR and International Statistical Classification of Diseases and Health Related Problems 10th Revision (ICD-10) Classification of Mental and Behavioral Disorders. The symptoms are scored by assigning a severity estimate for each symptom on a 4-point scale. The SNAP-IV rating is performed by the parent or legal

representative at each visit. The ratings from the SNAP-IV scale are grouped into the following 4 subscales:

- ADHD-Inattention (items #1-9),
- ADHD-Hyperactivity/Impulsivity (items #10-18)
- ODD (items #19-26)
- ADHD-Combined subscale: (items #1 18)

Each subscale score is the average of the available item scores in the subscale. The SNAP-IV rating scale will be administered at Visit 3 and Visit 6.

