# 5.2.1 Clinical Global Impression (CGI) Scales

The CGI scale was developed to provide a brief, stand-alone assessment of the clinician's view of a subject's global functioning prior to and after administration of a SM (Guy 1976). Severity of illness (CGI-S) and global improvement (CGI-I) are both rated on a scale of 1 to 7 with 7 being "extremely ill" or "very much worse", respectively. Successful therapy is indicated by a lower overall score in subsequent testing. Investigators should consider their total clinical experience with children who have IA associated with ADHD and rate how severe the subject's condition is at the time.

- CGI-S will be evaluated by the Investigator at each visit on a 7-point scale with 1=Normal, 2=Borderline ill, 3=Mildly ill, 4=Moderately ill, 5=Markedly ill, 6=Severely ill, and 7=Extremely ill.
- CGI-I, relative to the condition at Baseline (Visit 1), will be evaluated by the caregiver and by the Investigator at each post-baseline visit on a 7-point scale with 1=Very much improved, 2=Much improved, 3=Minimally improved, 4=No change, 5=Minimally worse, 6=Much worse, and 7=Very much worse.

CGI-S will be assessed by the Investigator at Visit 1, Visit 3, Visit 4, Visit 5 and Visit 6. CGI-I will be assessed by the caregiver and the Investigator at Visit 4, Visit 5 and Visit 6.

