# **6** STATISTICAL METHODS

# 6.1 Statistical and Analytical Plans

Tabular summaries of the data collected during the study will be presented to provide a general description of the subjects studied and an overview of the Efficacy, PK and safety results. Data from all sites will be combined in the computation of these summaries and summaries will be presented by treatment group. Continuous variables will be summarized using descriptive statistics (number of subjects, mean, standard deviation [SD], median, and minimum and maximum values). Categorical (nominal) variables will be summarized using frequency tables (number and percentage of subjects in each category).

In addition to tabular summaries, subject data listings, as specified in Sections 16.2 and 16.4 of ICH Guidance E3, will be provided. Additional subject data listings to be provided for this study are listed under the relevant subsections below. All data analyses will be performed by the CRO after the study is completed and the database is released. Statistical programming and analyses will be performed using SAS® and/or other validated statistical software as required.

Complete details of the statistical analysis will be provided in a separate statistical analysis plan (SAP), which will be written, finalized, and approved prior to database lock and will be included in the Clinical Study Report (CSR) for this protocol. The statistical analysis plan will supersede the statistical analysis methods described in this clinical protocol. Any deviation from the statistical plan will be documented and described in the final report. If changes to principal features stated in the protocol are required, these will be documented in a protocol amendment. The final SAP will take into account any amendment to the protocol.

In general, the baseline value for a variable is defined as the last observation prior to the first dose of double-blind study medication, ideally Visit 3, but including the screening value, if necessary.

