#### SEVERITY OF ILLNESS:

Considering your total clinical experience with this particular population (*impulsive aggression comorbld with ADHD*), how severe is the subject's condition at this time?

(0) NOT ASSESSED	(1) Normal, not at all ill	(4) Moderateły ill
	(2) Borderline mentally ill	(5) Markedly ill
	(3) Mildly ill	(6) Severely ill
		$\square$ (7) Among the most extremely ill patients

GLOBAL IMPROVEMENT: Rate total improvement whether or not, in your judgment, it is due entirely to drug treatment. Compared to his/her condition at Visit 1/Baseline, how much has the subject's *impulsive aggression* changed?

(0) NOT ASSESSED	(1) Very much improved	(4) No change
	(2) Much improved	(5) Minimally worse
2	(3) Minimally improved	(6) Much worse
		(7) Very much worse

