1 INTRODUCTION

The purpose of this statistical analysis plan (SAP) is to ensure the credibility of the study findings by specifying the statistical approaches to the analysis of the data prior to database lock. This SAP covers the planned analyses of all data collected on the eCRFs and diary pages, and will identify handling of data issues. The statistical analysis plan presented in this document will supersede the statistical analysis methods described in the clinical protocol. Any deviations/changes from the planned analyses described in this SAP will be identified, with justification, in the appropriate section of the clinical study report. This SAP is based on the clinical study protocol 810P302, version 7.0, dated 29 March 2019 and its associated electronic case report forms (eCRF).

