 - a. Inattention ratings
 - b. Hyperactivity/Impulsivity ratings
 - c. Oppositional Defiant Disorder
 - d. Combined Scale ratings
- 5. Percentage of responders with 50% or more reduction in the frequency of IA from baseline to treatment period (Table 14.2.2.7)
- 6. Percentage of responders with 30% or more reduction in the frequency of IA from baseline to treatment period (Table 14.2.2.8)
- 1.

Scores of CGI-I (investigator and caregiver) will be analyzed using a Mixed-Effect Model for Repeated Measure (MMRM) similar to the key secondary outcome. CGI-S will be used as baseline covariate.

Scores for CHQ-PF28, PSI-4-SF, and SNAP-IV will be analyzed using analysis of covariance (ANCOVA) on the ITT population. The model includes treatment and baseline as fixed independent covariates and Visit 6 value as a response variable. The least squares mean of each treatment group, the difference in the least squares mean (SPN-810 36 mg dose minus placebo), and the 2-sided 95% CI for the difference will be obtained.

The SAS code for the ANCOVA will be:

```
PROC MIXED DATA=XXXX ;

CLASS trtp usubjid;

MODEL Response = base trtp / DDFM=kr ;

LSMEANS trtp t/PDIFF=control ('PLACEBO') ALPHA=0.05;

RUN ;
```

Where usubjid is subject ID, trtp is treatment variable and Response is CHQ-PF28, PSI-4-SF, and SNAP-IV at Visit 6.

The Percentage of responders defined as 50% or more reduction (and 30% or more reduction) in the frequency of IA from baseline to treatment period will be analyzed using the logistic regression model with treatment as explanatory variables. Odds ratio (36 mg Dose / Placebo), and 95% CI for the odds ratio and p-value will be presented. In addition, the number and percentage of responders will be tabulated.

```
An example of SAS code follows.

ODS OUTPUT OddsRatios=or /* ODDS RATIO AND 95% CL*/

LSMeans=lsm(keep=trtpn mu) /* PROB OF RESPONDERS */ ;

PROC LOGISTIC DATA=ef1 PLOTS=none ;

CLASS siteid trtpn / PARAM=glm ;

MODEL avalc(EVENT="Yes")=trtpn;

LSMEANS trtpn / PDIFF=controll('2') ILINK ;

RUN;
```

To control family-wise error rate at 0.05 for multiple endpoints, the key secondary endpoint and additional secondary endpoints will be ordered as follows: CGI-S, investigator CGI-I, CHQ-PF28, PSI-4-SF, caregiver CGI-I, SNAP-IV ADHD, Percentage of responders with 50% or more reduction in the frequency of IA, percentage of responders with 30% or more reduction in the frequency of IA. The testing will proceed in the following order.

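### The SAP defines CGI-I as change since Visit 3, while the current protocol and the rating form ask for change since Visit 1, 15 to 45 days earlier and before the first dose

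*SAP*

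**What the plan says.** SAP 5.2.2 (Additional Secondary Variables): "CGI-I, relative to the condition at Visit 3, will be evaluated by the caregiver" and by the investigator at each post-baseline visit.

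Protocol 5.2.1: "CGI-I, relative to the condition at Baseline (Visit 1), will be evaluated by the caregiver" and by the investigator. The global improvement item on the form in Protocol Appendix 10.2 begins: "Compared to his/her condition at Visit 1/Baseline".

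SAP Section 1 leaves no doubt about which protocol should match: "This SAP is based on the clinical study protocol 810P302, version 7.0, dated 29 March 2019".

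CGI-I is analysed by MMRM. SAP 7.8.6.2 says "CGI-S will be used as baseline covariate" without naming a visit. The definitions table in SAP Section 4 supplies it: "Visit 3 CGI-S, CHQ-PF28, PSI-4-SF, and SNAP-IV are collected prior to the first dose", and those values serve as baseline in the covariate analyses. Protocol 6.1 likewise takes baseline as the "last observation prior to the first dose of double-blind study medication, ideally Visit 3", which sits awkwardly with the label that Protocol 5.2.1 attaches to Visit 1.

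In the testing order of SAP 7.8.6.2, investigator CGI-I comes directly after the key secondary CGI-S. Caregiver CGI-I is the fourth additional secondary endpoint.

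**The concern.** CGI-I is a change score that the rater forms mentally, so the reference visit is part of the endpoint definition. The analyst cannot move it afterwards by redefining baseline. The SAP supersedes the protocol's analysis methods, but it cannot alter the question printed on the form.

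If raters answered the printed question, each score covers the pre-treatment interval as well as treatment. A report that follows SAP 5.2.2 would then attribute any drift in that interval to the time since randomisation. This concerns investigator CGI-I, whose failure would leave the six later endpoints untested (CHQ-PF28, PSI-4-SF, caregiver CGI-I, SNAP-IV and the two responder rates), and also caregiver CGI-I itself. A second question follows: does a model holding only Visit 3 severity suit a score measured from Visit 1?

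**Working it through.** The plan states no figure that depends on this point, so there is none to reproduce. The check has two parts.

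**1. The texts side by side**

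| Place | Reference visit for CGI-I |
|---|---|
| Protocol 5.2.1 (v7.0) | Visit 1 |
| Protocol Appendix 10.2, form | Visit 1, also labelled baseline |
| SAP 5.2.2 | Visit 3 |
| Protocol 6.1, general baseline | Ideally Visit 3 |

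Distance between the anchors:
- Lower limit: Protocol 4.2.2 lets Visits 1 and 2 fall on the same day and puts Visit 2 at least 15 days before Visit 3, so the gap is at least 15 days.
- Upper limit: Protocol 3.2.1.2 caps screening plus baseline at 45 days.

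The form reads as the clinician's version. No caregiver form is shown, so the Visit 1 anchor for caregiver CGI-I rests on Protocol 5.2.1 alone.

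**2. What the Visit 3 covariate does for a Visit 1-anchored score**

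Document inputs: 306 randomised and about 121 on placebo (Protocol 6.10), hence 306 − 121 = 185 others. The 185 includes children randomised to 18 mg before that arm was dropped, so it overstates the 36 mg group. It serves only to set a scale.

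Assumptions, not document figures:
- severity S1 at Visit 1 has SD 1;
- S3 at Visit 3 has SD 1 and correlation ρ with S1 (0.5 or 0.8);
- S6 = 0.6·S3 + 0.8·e + effect, with e standard normal;
- the score is 4 + (S6 − S1), rounded and clipped to 1–7;
- the effect is 0 or −0.3.

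Apart from constants and rounding, the score is 0.6·S3 − S1 + 0.8·e. Its residual variance is:
- unadjusted: 0.36 + 1 − 1.2ρ + 0.64 = 2 − 1.2ρ, giving 1.40 and 1.04;
- adjusted for S3: (1 − ρ²) + 0.64, giving 1.39 and 1.00;
- adjusted for S1: 0.36(1 − ρ²) + 0.64, giving 0.91 and 0.77;
- adjusted for both: 0.64 and 0.64.

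Visit 3 severity alone removes almost nothing here. The standard error is larger than with both covariates by a factor √(1.39/0.64) = 1.47 at ρ = 0.5 and √(1.00/0.64) = 1.25 at ρ = 0.8.

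Simulation of the same model (4,000 replicates, linear model, 5% two-sided):

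| ρ | Covariate | Rejection, no effect | Mean estimate, effect −0.3 | Power |
|---|---|---|---|---|
| 0.5 | Visit 3 | 0.049 | −0.290 | 0.55 |
| 0.5 | Visit 1 | 0.050 | −0.292 | 0.72 |
| 0.8 | Visit 3 | 0.052 | −0.299 | 0.70 |
| 0.8 | Visit 1 | 0.048 | −0.299 | 0.80 |

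Type I error is at its nominal level and the estimates agree. Only precision differs. A separate illustration with other assumptions about rating noise (3,000 replicates) compared Visit 3 alone with both visits: power was 0.54 against 0.79 at ρ = 0.5, and 0.82 against 0.97 at ρ = 0.8. The direction is the same and the size differs.

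**The case against.** **The covariate.** A reader might infer that the model adjusts for the wrong visit and that the comparison is compromised. The documents do not support that. Visit 3 CGI-S is measured before the first dose and fits the general baseline definition in both documents. A covariate need not come from the rating's anchor visit for a randomised comparison to be valid, and the check above found no bias and no type I inflation. This objection stands. What remains is interpretation and precision.

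**A power loss from the anchor.** A reader might also add an assumed pre-treatment variance to an on-treatment variance and quote a loss of power. With an on-treatment SD of 1.2, pre-treatment SDs of 0.25 and 1.0 turn 80% power into 78% and 58%, so the answer mainly returns the assumption. The sum also treats the two changes as independent, whereas regression to the mean would make them negatively correlated. And it prices the form's own anchor, which correcting the SAP sentence would not recover. No such figure should be quoted.

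**Regression after selection at Visit 1.** Protocol 4.1.1 requires CGI-S of at least moderately ill at both Screening and Randomization, which limits drift. R-MOAS and the Vitiello scale are applied at screening only, so some drift remains possible. Its size is unknown.

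**Which anchor raters used.** The protocol's summary of changes shows that the CGI-I wording named Visit 3 before it was corrected to Visit 1. That superseded text is not an error, but the SAP line may be carried over from it, and some ratings may have been made under it. The form's joint label of Visit 1 and baseline can be read either way. It is therefore not established that every score contains pre-treatment change.

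**Effect on outputs.** The listed CGI-I tables are titled by score and visit, with no mention of Visit 3, and no derivation depends on the sentence. This too stands: the harm lies in how the endpoint is defined and described.

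**Conclusion.** The contradiction is real and lies in current text: Visit 1 in the protocol and on the form, Visit 3 in the SAP, 15 to 45 days apart and all before treatment. It affects the stated meaning of the first additional secondary endpoint in the gated sequence and of the fourth. The randomised comparison is valid under either reading.

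If the anchor is Visit 1, adjusting for Visit 3 CGI-S alone forgoes precision. The size depends on assumed correlations, and the figures above are illustrative. They treat severity as measured without error and ignore the CGI-S entry criterion, which narrows the covariate's range, so the real gain may be smaller. The point should be fixed before unblinding, but it does not threaten the trial's conclusions.

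**What to change.** 1. Reconcile Protocol 5.2.1, Protocol 6.1, Appendix 10.2 and SAP 5.2.2 to the anchor that investigators and caregivers were actually given. The current protocol and form indicate Visit 1. Confirm the caregiver instruction separately.
2. If it is Visit 1, correct the sentence in SAP 5.2.2 and describe CGI-I results as improvement since Visit 1.
3. In SAP 7.8.6.2, name the visits of the CGI-S covariates and, for a Visit 1 anchor, include both Visit 1 and Visit 3 CGI-S in the CGI-I MMRM.
4. If some ratings were made under a Visit 3 instruction, flag them and repeat the CGI-I analysis without them as a sensitivity analysis.

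The cost is a few sentences, one more covariate and possibly one sensitivity table. Protocol 5.2.1 already schedules CGI-S at both visits, so no new data are needed.
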